# Analysis of Hypoglycemia

The Tier 1 analysis for hypoglycemia, which will be used to address the objectives and hypotheses related to hypoglycemia, will include the numbers and percentages of patients experiencing one or more adverse events of symptomatic hypoglycemia, regardless of biochemical documentation.

The Tier 2 analysis for hypoglycemia will include the numbers and percentages of patients experiencing one or more of each the following:

- Adverse events of hypoglycemia (symptomatic or asymptomatic), regardless of biochemical documentation.
- Adverse events of documented hypoglycemia, defined as adverse events of symptomatic hypoglycemia with a concurrent glucose measurement of  $\leq 70 \text{ mg/dL}$  ( $\leq 3.9 \text{ mmol/L}$ ).

Protocol/Amendment No.: 002-01

 Adverse events of severe hypoglycemia, defined as adverse events of symptomatic hypoglycemia that required assistance, either medical or non-medical, regardless of whether such assistance was obtained, and regardless of biochemical documentation. These events will be further sub-classified as:

- Those that required medical assistance. Adverse events of symptomatic hypoglycemia that included a markedly depressed level of consciousness, loss of consciousness, or seizure will be classified as having required medical assistance, whether or not medical assistance was obtained
- Those that did not require medical assistance (i.e., those episodes that required non-medical assistance to treat).

The Tier 3 summary of hypoglycemia will include the following, based on episodes classified by the investigator as adverse events:

- The numbers and percentages of patients with each of the following, overall and by lowest reported glucose category (<50 mg/dL [<2.8 mmol/L], ≤70 mg/dL [≤3.9 mmol/L], >70 mg/dL [>3.9 mmol/L], or unknown). A patient's lowest glucose category will be classified as unknown only if no glucose measurements are available for that patient.
  - 1. any episodes (symptomatic or asymptomatic)
  - 2. symptomatic episodes
  - 3. asymptomatic episodes
- The numbers and percentages of patients with episodes having precipitating factors
- The number of episodes per patient
- The number of each of the following (summed across all patients). The overall summary will include an indication of whether precipitating factors were present.
  - 1. all episodes (symptomatic or asymptomatic)
  - 2. symptomatic episodes
  - 3. asymptomatic episodes

Categorization of episodes by glucose level will be performed based on the units (mg/dL or mmol/L) in which the glucose measurements were recorded.

A summary of patients with episodes that were reported on the hypoglycemia assessment (HA) eCRF but were not classified by the investigator as adverse events will also be provided. If a substantial number of patients had episodes that were not classified as adverse events, then additional summaries may be provided for the Tier 3 endpoints above, including all episodes reported on the HA eCRF (i.e., not restricted to adverse events). It is expected that all symptomatic hypoglycemia episodes will be classified by the investigator as adverse events and, thus, any episodes that are not classified as adverse events will be asymptomatic episodes.

**Protocol/Amendment No.:** 002-01

# 8.2.4 Summaries of Baseline Characteristics, Demographics, and Other Analyses

The comparability of the treatment groups at baseline for each relevant characteristic will be assessed by the use of tables and/or graphs. No statistical tests will be performed on these characteristics. The number and percentage of subjects screened, randomized, the primary reasons for screen failure, and the primary reason for discontinuation will be displayed. Medical history and prior and concomitant therapies will be summarized by treatment either by descriptive statistics or categorical tables. In addition, the following demographic/anthropometric, diabetes-related, and baseline efficacy variables will be summarized by treatment either by descriptive statistics or categorical tables. Depending on the variable of interest, statistics such as sample size, mean, SD, median, range and proportion will be provided.

- Continuous baseline demographic variables: age (years), weight (kg), height (cm), and body mass index (BMI; kg/m^2).
- Categorical baseline demographic variables: age (<65 years, ≥65 years), gender (male, female), and race (White, Black, Asian, American Indian or Alaska Native, Native Hawaiian or Other Pacific Islander, or Multi-Racial), ethnicity (Hispanic/Latino or not).
- Baseline A1C, and distribution of A1C at baseline (A1C levels <7%,  $\ge7\%$  and <8%,  $\ge8\%$ )
- Baseline FPG
- Baseline HOMA-%β
- Prior antihyperglycemic medication (monotherapy or dual therapy)
- Time since diagnosis of diabetes mellitus (years)
- Geographic region (Asia, Europe [including Russia] or North America [U.S. and Canada])

The above summaries will be provided for all subjects who received at least one dose of study therapy.

# 8.2.5 Multiplicity

The family-wise type I error rate will be controlled at  $\alpha$ =0.05 (2-sided) using the testing procedure depicted in Figure 2.

The first six tests will be conducted in a fixed sequence at  $\alpha$ =0.05 (2-sided). The non-inferiority hypothesis will be tested using the 95% 2-sided confidence interval (CI) rather than a p-value. If, and only if, all of the first six success criteria are met, the next two tests will be conducted and will use the Hochberg procedure [17]. If, and only if, both tests in the Hochberg procedure are successful, superiority of ertugliflozin to glimepiride will be assessed for the A1C endpoint. This assessment will be performed for each dose of ertugliflozin following a fixed sequence using  $\alpha$ =0.05 (2-sided) for each test.

[figure not shown]

Figure 2 Multiplicity Schema

Comparisons involving other efficacy endpoints and time points are considered supportive and will be made at the  $\alpha$ =0.05 nominal level (two-sided). No multiplicity adjustment will be performed on these other comparisons.

From a safety standpoint, application of a multiplicity adjustment could potentially mask a safety concern. Thus, no control of Type I error rate beyond the per-comparison  $\alpha$ =0.05 nominal level (i.e. 95% CI) will be applied to the safety analyses, with the realization that spurious statistical significance may be observed for some endpoints.

MK-8835-002-01 Final Protocol

Output

# 8.2.6 Sample Size and Power Calculations

This trial will randomize approximately 1230 subjects into three treatment groups in a 1:1:1 ratio. A sample size of 410 per arm will be equivalent to an effective sample size of 337 per arm at Week 52 in the power calculation for the primary hypothesis test using the cLDA model in the FAS population. The effective sample size accounts for information loss due to missing data and the correlation among repeated measures, and is derived using the method proposed by Lu, et al. [21] under the assumptions of cumulative attrition rates and covariance matrix at Weeks 6, 12, 18, 26, 39 and 52 specified below. An effective sample size 337 per arm will provide 97% power to declare non-inferiority for a margin=0.3% in A1C reduction at Week 52 assuming the true mean difference in A1C between a given ertugliflozin dose level and glimepiride is 0% ( $\alpha$ =0.05, two-sided test) and the conditional standard deviation is 1.0% (Table 14).

The half-width of the 95% CI is expected to be 0.15%. The power for achieving success for both ertugliflozin doses will be approximately 95%. In the per-protocol population, the expected sample size is approximately 63% of the randomized population (257 subjects per arm).

Table 14 Power to Declare Non-inferiority in A1C at Week 52

		Power		95% CI
Population	N per Arm	Per Comparison	Both Comparisons	Half-width
FAS	337 †	97%	95%	0.15%
PP	257	92%	85%	0.17%

†Effective sample size, accounting for missing data and within-subject correlation of A1C over time. Based on a non-inferiority margin ( $\delta$ ) = 0.3%, true difference = 0%, standard deviation = 1%, and  $\alpha$  = 0.05 (2-sided).

Assumptions for the cumulative attrition rates and correlation matrix at Week 6, 12, 18, 26, 39 and 52 are listed below:

- Cumulative attrition rates at Weeks 6, 12, 18, 26, 39 and 52 are 0.073, 0.091, 0.112, 0.160, 0.210, and 0.312, respectively
- Conditional correlation matrix at Weeks 6, 12, 18, 26, 39 and 52 is

1	0.83	0.71	0.67	0.57	0.57
0.83	1	0.89	0.80	0.68	0.66
0.71	0.89	1	0.90	0.76	0.73
0.67	0.80	0.90	1	0.81	0.77
0.57	0.68	0.76	0.81	1	0.85
0.57	0.66	0.73	0.77	0.85	1

The above assumptions are derived based on data from MK-0431 P024.

Table 15 provides the detectable difference at 90% power for endpoints in the secondary hypotheses in the FAS population.

Protocol/Amendment No.: 002-01

Table 15 Power Calculations for Key Secondary Endpoints in the FAS Population

Endpoint	Effective Sample Size per Arm	Variability Measurement	Detectable Difference at 90% Power
Proportion of subjects with symptomatic hypoglycemia AEs	410	Proportion for ertugliflozin=5% †	6.2%
Change from baseline in body weight	331	$SD=4.3 \text{ kg}^{\dagger}$	1.1 kg
Change from baseline in systolic BP	337	SD=11.2 mm Hg ‡	2.8 mm Hg
† Based on canagliflozin study DIA3009.			•
‡ Based on canagliflozin study DIA3012.			

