## 3.2 Secondary Objective(s) & Hypothesis(es)

In subjects with T2DM and inadequate glycemic control on metformin, after 52 weeks:

(1) **Objective:** To assess the effect of the addition of ertugliflozin 15 mg q.d. compared with the addition of glimepiride on the incidence of symptomatic hypoglycemia.

**Hypothesis:** The addition of ertugliflozin 15 mg q.d. leads to a lower incidence of symptomatic hypoglycemia compared with the addition of glimepiride.

(2) **Objective:** To assess the effect of the addition of ertugliflozin 15 mg q.d. compared with the addition of glimepiride on change in body weight from baseline.

**Hypothesis:** The addition of ertugliflozin 15 mg q.d. decreases body weight compared with the addition of glimepiride.

(3) **Objective:** To assess the A1C-lowering efficacy of the addition of ertugliflozin 5 mg q.d. compared with the addition of glimepiride.

**Hypothesis:** The change from baseline in A1C in subjects treated with ertugliflozin 5 mg q.d. is non-inferior compared with that in subjects treated with glimepiride.

(4) **Objective:** To assess the effect of the addition of ertugliflozin 5 mg q.d. compared with the addition of glimepiride on the incidence of symptomatic hypoglycemia.

**Hypothesis:** The addition of ertugliflozin 5 mg q.d. leads to a lower incidence of symptomatic hypoglycemia compared with the addition of glimepiride.

(5) **Objective:** To assess the effect of the addition of ertugliflozin 5 mg q.d. compared with the addition of glimepiride on change in body weight from baseline.

**Hypothesis:** The addition of ertugliflozin 5 mg q.d. decreases body weight compared with the addition of glimepiride.

(6) **Objective:** To assess the effect of the addition of ertugliflozin 15 mg q.d. compared with the addition of glimepiride on systolic blood pressure.

**Hypothesis:** The addition of ertugliflozin 15 mg q.d. reduces systolic blood pressure compared with the addition of glimepiride.

(7) **Objective:** To assess the effect of the addition of ertugliflozin 5 mg q.d. compared with the addition of glimepiride on systolic blood pressure.

**Hypothesis:** The addition of ertugliflozin 5 mg q.d. reduces systolic blood pressure compared with the addition of glimepiride.

**Product:** MK-8835 26

**Protocol/Amendment No.:** 002-01

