# 8.1.3 Multiplicity

The type I error rate will be controlled at  $\alpha$ =0.05 level (2 sided) for all efficacy hypotheses via a combination of ordered testing and the Hochberg procedure [17] as follows. This strategy is depicted in Figure 2.

- Ordered testing ( $\alpha$ =0.05) for the following 6 tests:
  - o A1C non-inferiority, ertugliflozin 15 mg vs. glimepiride
  - o Hypoglycemia superiority, ertugliflozin 15 mg vs. glimepiride
  - o Body weight superiority, ertugliflozin 15 mg vs. glimepiride
  - o A1C non-inferiority, ertugliflozin 5 mg vs. glimepiride
  - o Hypoglycemia superiority, ertugliflozin 5 mg vs. glimepiride
  - o Body weight superiority, ertugliflozin 5 mg vs. glimepiride
- If the success criterion is achieved for all of the above six tests, the Hochberg procedure ( $\alpha$ =0.05 or 0.025) will be used for the following two tests:
  - o Systolic blood pressure superiority, ertugliflozin 15 mg vs. glimepiride
  - o Systolic blood pressure superiority, ertugliflozin 5 mg vs. glimepiride
- If the success criterion is met for both of the above two tests for systolic blood pressure, then the following two tests will be conducted in order ( $\alpha$ =0.05):
  - o A1C superiority, ertugliflozin 15 mg vs. glimepiride
  - o A1C superiority, ertugliflozin 5 mg vs. glimepiride.

**Protocol/Amendment No.:** 002-01

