# **8.2.3.1** Statistical Methods for Efficacy Analyses

# Phase A (Week 0 to Week 52)

The primary efficacy analyses will compare the efficacy of ertugliflozin relative to glimepiride in change from baseline in A1C at Week 52. The mean change from baseline in A1C at Week 52 in the ertugliflozin 15 mg group will be compared to that in the glimepiride group using the estimated treatment difference via a constrained longitudinal data analysis (cLDA) model, proposed by Liang and Zeger [15]. This cLDA model assumes a common mean across treatment groups at baseline and a different mean for each treatment at each of the post-baseline time points. In this model, the response vector consists of baseline values and the values observed at each post-baseline time point. The cLDA model will include terms for treatment, time, prior antihyperglycemic medication (monotherapy or dual therapy), baseline eGFR, and the interaction of time by treatment. Time will be treated as a categorical variable so that no restriction is imposed on the trajectory of the means over time. The treatment difference in terms of mean change from baseline to a given time point will be estimated and tested from this model. Ertugliflozin 15 mg will be declared non-inferior to glimepiride in terms of A1C reduction if the upper limit of the two-sided 95% confidence interval (CI) for the mean difference between ertugliflozin 15 mg and glimepiride at Week 52 is less than the non-inferiority margin,  $\delta$ =0.3%. This margin was chosen because changes from baseline smaller than -0.3% have limited clinical impact, and the 0.3% margin balances lesser clinical impact with a study sample size that is feasible to conduct. The non-inferiority test for ertugliflozin 5 mg in A1C reduction will use the same approach described above following the multiplicity control strategy in Section 8.2.5. If non-inferiority is declared for ertugliflozin 15 mg, then an assessment of superiority will be conducted following the multiplicity control strategy described in Section 8.2.5. For the cLDA model, the Kenward-Roger adjustment will be used with restricted (or residual) maximum likelihood (REML) to make proper statistical inference. An unstructured covariance matrix will be used to model the correlation among repeated measurements and hence avoids the potential bias that could result from the use of specific structured covariance models. If the unstructured covariance model fails to converge with the default Newton-Raphson algorithm, the Fisher scoring algorithm or other appropriate methods can be used to provide initial values of the covariance parameters. In the rare event that none of the above methods yield convergence, a structured covariance such as Toeplitz can be used to model the correlation among repeated measurements. In this case, the empirical option will be used because the sandwich variance estimator is asymptotically unbiased while the model-based variance estimator can substantially overestimate or underestimate the true variance. The cLDA model uses the maximum likelihood principle to estimate the parameters and account for missing data in an implicit fashion. Values of eGFR that are >120 mL/min/1.73 m^2 will be set to 120  $mL/min/1.73 m^2$ .

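### The stated 97% power to declare A1C non-inferiority holds for ertugliflozin 15 mg only; for 5 mg, tested fourth, it is at most about 95% under the plan's own assumptions

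*Combined protocol and SAP*

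**What the plan says.** Section 8.2.6 states: "An effective sample size 337 per arm will provide 97% power to declare non-inferiority for a margin=0.3% in A1C reduction at Week 52". The sentence assumes a true difference of 0% for either ertugliflozin dose and a conditional standard deviation of 1.0%. Section 8.1.4 gives the same 97%, also for either dose. The table that holds the figures is headed "Table 14 Power to Declare Non-inferiority in A1C at Week 52". Its columns are labelled per comparison (97% FAS, 92% per-protocol) and both comparisons (95% FAS, 85% per-protocol).

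On the two doses together, Section 8.2.6 says "The power for achieving success for both ertugliflozin doses will be approximately 95" per cent. Section 8.1.4 describes the same 95% more carefully, as a probability of meeting the criterion.

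The testing rules are in Section 8.2.5: "The first six tests will be conducted in a fixed sequence". Section 8.1.3 lists the order, and "A1C non-inferiority, ertugliflozin 5 mg vs. glimepiride" is fourth, after the 15 mg tests of A1C, hypoglycemia and body weight. Section 8.2.3.1 confirms that the 5 mg test uses the approach "described above following the multiplicity control strategy in Section 8.2.5".

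The 5 mg comparison is a formal secondary hypothesis. Section 3.2, item 3, states that the A1C change "in subjects treated with ertugliflozin 5 mg q.d. is non-inferior compared with that in subjects treated with glimepiride".

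**The concern.** A test that comes fourth in a fixed sequence leads to a formal claim only if the three tests before it succeed. One of those three is the 15 mg A1C test. Declaring 5 mg non-inferior therefore always means that 15 mg has been declared as well, and that 15 mg has also succeeded on hypoglycemia and body weight. The power to declare 5 mg cannot be the stand-alone 97%, yet both power sections and the table title use the language of declaring, and none of them says that the sequence is left out.

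A reader planning on the 5 mg secondary hypothesis would take 97% as its chance of formal success. That is above what the design can deliver under its stated assumptions. The reader would also not learn that the figure depends on two other endpoints.

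**Working it through.** **Inputs (Section 8.2.6 and Table 14).** Effective n per arm 337 (FAS) and 257 (per-protocol); SD 1.0; margin 0.3; true difference 0 for each dose; two-sided alpha 0.05, so z = 1.96. Allocation is 1:1:1, and one glimepiride arm serves both comparisons, so the two A1C test statistics have correlation 0.5.

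**1. Reproduce the plan's FAS figures.**
- Standard error = sqrt(2/337) = 0.0770. CI half-width = 1.96 × 0.0770 = 0.151 (plan: 0.15).
- Per comparison: 0.3/0.0770 − 1.96 = 3.894 − 1.960 = 1.934, and Φ(1.934) = 0.9735 (plan: 97%).
- Both doses: bivariate normal probability that both statistics fall below 1.934, correlation 0.5 = 0.9519. If independent, 0.9735² = 0.9476. Either rounds to the plan's 95%.

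The stated 97% and 95% come from the A1C inputs alone, with no testing sequence.

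**2. Add the sequence.** Under Sections 8.1.3 and 8.2.5:

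P(declare 5 mg) = P(15 mg A1C, 15 mg hypoglycemia, 15 mg weight and 5 mg A1C all succeed) ≤ P(both A1C criteria are met) = 0.952.

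For 15 mg, tested first, P(declare) = 0.973, as printed. For 5 mg the certain gap is 97.3 − 95.2 = 2.1 points. The bound is reached only if the 15 mg hypoglycemia and weight tests are certain to succeed.

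**3. Can the remaining loss be worked out?** It needs the power of the 15 mg hypoglycemia and weight tests at their expected effects. Table 15 gives the differences detectable at 90% power (6.2 points and 1.1 kg), not expected effects. Section 4.2.1 gives a direction, since it associates sulfonylureas with hypoglycemia and weight gain, but no size. The loss cannot be computed from the documents.

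**4. Dependence on the equal-dose assumption.** The 95.2% needs zero true difference for both doses. If 5 mg equals glimepiride and 15 mg is better by 0.02 points, the limit for 15 mg becomes 0.32/0.0770 − 1.96 = 2.194 and the joint probability is 0.963. At 0.05 points the limit is 2.583 and the joint probability is 0.970. These gaps are illustrations, not figures from the plan.

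**5. Per-protocol figures.** Standard error = sqrt(2/257) = 0.0882; 0.3/0.0882 − 1.96 = 1.441; Φ(1.441) = 0.9252 (plan: 92%). Both doses: 0.9252² = 0.856 if independent, which is close to the plan's 85% (0.854 as a product of t-test powers). With correlation 0.5 it is 0.872, that is 87%. The printed 85% therefore treats the two comparisons as independent and is slightly conservative.

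**The case against.** The strongest reply is that nothing is miscalculated and most of the labelling is already there. Table 14's columns separate per-comparison from both-comparison figures. The 95% is printed beside the 97% and repeated in both text sections. Section 8.2.6 introduces the calculation as one for the primary hypothesis test, and the primary A1C hypothesis in Section 3.1 concerns 15 mg only. Per-comparison power is a common way to report secondary tests.

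Much of this stands. It shows that the 97% is a sound marginal figure and that the defect is one of wording. It does not remove the defect: both text sections extend the 97% to either dose, they and the table title speak of declaring, and nothing says that the sequence is excluded. A column label does not tell the reader that a 5 mg claim also needs success on hypoglycemia and weight at 15 mg.

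A second reply also stands: the 95.2% ceiling depends on the doses being equal. Table 2 models a larger A1C response at 15 mg than at 5 mg (94% against 83% of maximum), and a small 15 mg advantage brings the ceiling back to about 97%. The ceiling must therefore be stated as conditional on Table 14's assumption.

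A reader might go further and put the 5 mg power at about 77%, by giving each 15 mg gate test the 90% power in Table 15 (0.952 × 0.90 × 0.90 = 0.771). The documents do not support that. It treats detectable differences as expected effects and assumes that the endpoints are independent. If the true effects are large, the loss below 95% is negligible.

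**Conclusion.** The point holds as a mislabelled power figure. The 97% is correct for declaring 15 mg. For 5 mg it is a per-comparison probability of meeting the A1C criterion. With zero true difference for both doses, SD 1.0 and 337 effective subjects per arm, the power to declare 5 mg is at most 95.2%, about 2 points below the stated figure. It is lower by whatever chance there is that the 15 mg hypoglycemia or weight test fails; the plan does not allow that amount to be stated.

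Two inferences should be avoided. The printed 95% is not itself the power to declare 5 mg: it ignores the two gate tests and is only an upper limit. Nor do the documents show that the trial is underpowered for 5 mg. The testing procedure is unchanged, so type I error and the validity of the analysis are not affected.

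The per-protocol both-dose figure is a separate, minor matter: 87% with the shared arm, against 85% printed.

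**What to change.** 1. In Sections 8.1.4 and 8.2.6, limit the statement of 97% power to declare non-inferiority to 15 mg. Retitle Table 14 *Probability of meeting the A1C non-inferiority criterion at Week 52*. Add: *These figures do not include the Section 8.2.5 testing sequence. With zero true difference for both doses, the power to declare non-inferiority for 5 mg is at most about 95% and also depends on success of the 15 mg hypoglycemia and body weight tests.*
2. Minor: in Section 8.1.4 and Table 14, change the per-protocol both-dose figure from 85% to 87%, to reflect the shared glimepiride arm.

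The cost is a few words of text, one table title and one table cell. Sample size, alpha, order of tests and analysis stay as they are.

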# 8.1.4 Power and Sample Size

The trial will randomize approximately 1230 subjects in a 1:1:1 ratio among the 3 treatment groups. A sample size of 410 per arm will provide 97% power to declare non-inferiority in A1C reduction at Week 52 between a given ertugliflozin dose and glimepiride, using a non-inferiority margin of 0.3%, assuming the true mean difference in A1C is 0%, based on the primary analysis population (FAS). The half-width of the 95% CI is expected to be 0.15%. The probability of meeting the non-inferiority criterion for both ertugliflozin doses in the FAS is 95%. In the secondary analysis population (Per-protocol), the power for declaring non-inferiority is 92% per dose, and 85% for both doses. The above calculations are based on the variability and subject attrition assumptions specified in Section 8.2.6.

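### Table 15's 2.8 mm Hg at 90% power for systolic blood pressure is a single unadjusted comparison, not the planned gated Hochberg test; separately, per-protocol power for both doses is about 87%, not 85%

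*Combined protocol and SAP*

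**What the plan says.** Section 8.2.6 introduces the secondary power figures with "Table 15 provides the detectable difference at 90% power for endpoints in the secondary hypotheses in the FAS population". The systolic pressure row, "Change from baseline in systolic BP", lists an effective 337 subjects per arm, an SD of 11.2 mm Hg and a detectable difference of 2.8 mm Hg. Neither the table nor its introduction gives an alpha or mentions the testing procedure.

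Section 8.2.5 places systolic pressure behind a gate: "If, and only if, all of the first six success criteria are met, the next two tests will be conducted". The six are A1C non-inferiority, hypoglycemia and body weight, for 15 mg and then for 5 mg. Section 8.1.3 specifies Hochberg for the two systolic tests, at 0.05 or 0.025. Success on both of them opens the A1C superiority tests.

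For A1C non-inferiority in the per-protocol population, section 8.1.4 gives power of "92% per dose, and 85% for both doses", and Table 14 repeats it for 257 subjects per arm. The method behind the joint figure is not stated. Both doses are compared with the same glimepiride arm, with 1:1:1 allocation.

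**The concern.** Systolic pressure for each dose is a stated secondary hypothesis (section 3.2, hypotheses 6 and 7). It is also the only Table 15 endpoint tested by Hochberg, and it stands last in line before A1C superiority. Table 14 separates per-comparison power from power for both comparisons, but Table 15 carries no such label. Someone planning around a 2.8 mm Hg effect could read the row as a 90% chance of a confirmatory claim, which the planned procedure does not give.

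The per-protocol question is separate and runs the other way. Two comparisons that share a control arm are positively correlated, so the chance that both succeed is higher than the product of the two powers. The stated 85% looks too low for 92% per dose.

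**Working it through.** **Inputs.** Systolic pressure: n = 337 per arm, SD 11.2, difference 2.8 (Table 15). Body weight: n = 331, SD 4.3 kg, difference 1.1 kg (Table 15). Hypoglycemia: n = 410, 5% on ertugliflozin, difference 6.2 points (Table 15). A1C: margin 0.3%, true difference 0, SD 1%, n = 337 in the FAS and 257 per protocol (Table 14). With equal arms and a shared control, the correlation between the two dose comparisons is 0.5.

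**1. Reproduce the systolic row.** SE = 11.2 × √(2/337) = 0.863.
- Two-sided 0.05: (1.960 + 1.282) × 0.863 = 2.80 mm Hg, and power at 2.8 is 90.1%. This matches.
- Two-sided 0.025: power at 2.8 is 84.2%, and the 90% value is (2.241 + 1.282) × 0.863 = 3.04 mm Hg. This does not match.
- One-sided 0.05: power is 94.5%. This does not match.

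So the row is one unadjusted two-sided 0.05 comparison.

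**2. Hochberg step alone.** A dose is declared if both statistics exceed 1.960, or if its own exceeds 2.241. At 2.8 mm Hg the mean of the statistic is 2.8/0.863 = 3.245. Then

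P(declare one dose) = P(Z₁ > 2.241) + P(both > 1.960) − P(Z₁ > 2.241 and Z₂ > 1.960).

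| True effect | Power for a dose with the effect | Both doses declared | Difference needed for 90% per dose |
|---|---|---|---|
| 2.8 mm Hg at both doses | 0.842 + 0.833 − 0.787 = 88.9% (unrounded sum) | 83% | about 2.85 mm Hg |
| 2.8 mm Hg at one dose, 0 at the other | about 84% | – | about 3.04 mm Hg |

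**3. Six-test gate.** This step assumes independent endpoints, correlation 0.5 between doses within an endpoint, and a true A1C difference of 0.
- A1C non-inferiority: 97.3% per dose, 95.2% for both.
- Hypoglycemia at 6.2 points: 90.4% per dose, 83.8% for both.
- Weight at 1.1 kg: 90.8% per dose, 84.5% for both.

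| Hypoglycemia and weight effects | Gate passes | Systolic claim, per dose | Systolic claim, both doses |
|---|---|---|---|
| At Table 15's detectable differences | 0.952 × 0.838 × 0.845 = 67% | 0.674 × 0.889 = 60% | 0.674 × 0.833 = 56% |
| All four tests certain to succeed | 95.2% | 0.952 × 0.889 = 85% | 0.952 × 0.833 = 79% |

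**4. Per-protocol power for both doses.** SE = √(2/257) = 0.0882, and 0.3/0.0882 − 1.960 = 1.441.
- Per dose: 92.5% (92.4% by t). The plan's 92% is consistent with the t value.
- Both doses with correlation 0.5: 87.2% (87.0% by t).
- Both doses as a product: 0.925² = 85.6% (85.4% by t).
- Lower bound 2p − 1, valid under any correlation: 85.0% (84.9% by t).

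In the FAS, the product (94.8%) and the correlated value (95.2%) both round to the stated 95%, so that figure needs no change.

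**The case against.** The strongest reply is that no figure in Table 15 is miscalculated. The 2.8 mm Hg is right for a single comparison, per-comparison reporting is common, and the gate and the Hochberg step are set out in full in sections 8.1.3 and 8.2.5. All of that stands. What remains is that the row states neither its alpha nor its per-comparison basis, and the planned test does not have 90% power at 2.8 mm Hg.

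The Hochberg cost is also small, about one point, if both doses have the effect. The plan hypothesises an effect at both, and the Phase II reductions in section 4.1.2.1 (3.69, 2.77 and 2.77 mm Hg at 5, 10 and 25 mg) do not point to a dose without effect. The 3.04 mm Hg is therefore an upper case, not the expected one.

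Two stronger readings are tempting, and the documents support neither.
- A reader might infer that the plan's own assumptions give only about a 60% chance of a systolic claim. Table 15 lists detectable differences, not assumed true effects, and nothing in the plan says that the endpoints are independent. Larger hypoglycemia or weight effects move the figure towards 85%, and positive correlation between endpoints would also raise it.
- A reader might infer that the plan treated the two dose comparisons as independent. The 85% fits the t-based product (85.4%), but it fits the 2p − 1 bound (85.0%) just as well. The method cannot be identified from the text.

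**Conclusion.** The point holds as a gap between stated power and planned procedure, not as a calculation error in the systolic row. At 2.8 mm Hg, the Hochberg step gives 88.9% per dose if both doses have that effect and about 84% if only one does. These values rest only on the plan's n and SD and on the 0.5 correlation from the shared arm.

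The probability through the whole sequence is about 60% to 85% per dose under the two scenarios worked out. That range rests on assumptions that the documents do not make: independent endpoints, and the chosen hypoglycemia and weight effects. It is a sensitivity range, not a property of the design.

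The per-protocol figure of 85% is not the joint power under the stated inputs, which is about 87%. Whatever method produced it, it is conservative by about 2 points and concerns a secondary population. The 97% primary power, the sample size and the control of type I error are unaffected.

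**What to change.** - **Table 15:** state that the entries are per-comparison values at unadjusted two-sided 0.05.
- **Systolic pressure row:** add the difference detectable with 90% power under the Hochberg step, about 2.85 mm Hg if both doses have the effect and up to 3.04 mm Hg if only one does.
- **Full-sequence probability, if one is given:** show it as a range of about 60% to 85% per dose, with the assumptions on A1C, hypoglycemia, weight and independence beside it. Do not print a single number.
- **Section 8.1.4 and Table 14:** restate per-protocol power for both doses as 87%, and note the 0.5 correlation.

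The cost is a text change to two tables and one section. The added systolic figures are less favourable than the present one, and the per-protocol figure is slightly more favourable. No extra subjects and no change to any analysis are needed.
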